6.2.3. Day 1 and 7 (Telephone Call Follow-Up)

Telephone call follow-ups will be conducted by an HF nurse, or designee, on Days 1 and 7 post discharge from the ED. The primary purpose of the follow-up telephone calls will be to evaluate the safety and efficacy of diuresis and the need to adjust diuretic therapy. The telephone follow-up will be guided by a suggested Telephone Script. Assessments during each phone call will include:

- Suggested Telephone Script to review Subject Diary
- Infusor start and stop time for each dose
- Change in diuretic treatment since last point of contact (record on concomitant medication form)
- Assessment for adverse events
- Assessment for interval hospitalizations, emergency department visits, or unscheduled clinic visits
 - Been admitted to the hospital
 - Been admitted to the hospital for HF-related issues
 - Been seen at the emergency department for HF-related issues
 - Been seen in an outpatient clinic (including immediate care clinic) for HF-related issues
 - Sought any additional or new medical treatment for HF-related issues
- Problems with drug or device use

6.2.4. Day 2-4 (In-Clinic visit)

The following procedures/assessments will be performed at the Day 2-4 in-clinic visit:

- Interim medical history and medication review
- Cardiopulmonary Exam, focused on signs and symptoms of congestion
- NYHA Classification

- Weight obtained for BMI
- Vital Signs
- Venous blood for clinical chemistries, hematology, BNP or NT-proBNP
- Change in diuretic treatment since last point of contact (record on concomitant medication form)
- Assessment for selective electrolyte replacement (record on concomitant medication form)
- Comfort of Wear Questionnaire
- Abdominal skin assessment
- Assessment for adverse events
- Assess for interval hospitalizations, emergency department visits, or unscheduled clinic visits
 - Been admitted to the hospital
 - Been admitted to the hospital for HF-related issues
 - Been seen at the emergency department for HF-related issues
 - Been seen in an outpatient clinic (including immediate care clinic) for HF-related issues
 - Sought any additional or new medical treatment for HF-related issues
- Problem with drug or device use
- Review of Subject Diary for completeness
- Return of all used study devices

6.2.5. Days 14 – 21 (Telephone Call Follow-Up)

Telephone call follow-ups will be conducted by an HF nurse, or designee, as deemed necessary by the investigator between Days 14-21. The primary purpose of these calls will be to assess whether the subject has experienced or is experiencing a study related adverse event, to assess status of change back to oral medication, and to assess congestion.

The suggested script for conducting these telephone calls is the same that is described previously and will include:

- Suggested Telephone Script
- Additions or discontinuations of concomitant medications as per section 5.7 (record on concomitant medication form)
- Assessment for adverse events
- Assessment for interval hospitalizations, emergency department visits, or unscheduled clinic visits
 - Been admitted to the hospital
 - Been admitted to the hospital for HF-related issues
 - Been seen at the emergency department for HF-related issues
 - Been seen in an outpatient clinic (including immediate care clinic) for HF-related issues
 - Sought any additional or new medical treatment for HF-related issues
- Device start and stop time for each dose (if received study drug after Day 2-4 clinic visit)
- Problems with drug or device use (if received study drug after Day 2-4 clinic visit)

6.2.6. Day 30 ± 3 days (In-Clinic Visit)

The following procedures/assessments will be performed at the Day 30 in-clinic visit:

- Directed medical history and medication review
- Cardiopulmonary Exam focused on signs and symptoms of congestion
- NYHA Classification
- Weight for BMI
- Vital Signs

- Venous blood for clinical chemistries, hematology, BNP or NT-proBNP
- Administer the KCCQ-12
- Abdominal skin assessment
- Assessment of adverse events
- Assessment of interval hospitalization, emergency department visits, or unscheduled clinic visits
 - Been admitted to the hospital
 - Been admitted to the hospital for HF-related issues
 - Been seen at the emergency department for HF-related issues
 - Been seen in an outpatient clinic (including immediate care clinic) for HF-related issues
 - Sought any additional or new medical treatment for HF-related issues

Information regarding HF-related healthcare utilization collected before and at the 30-day in-clinic visit will be verified by the investigator through subjects' medical records.

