6. STUDY PROCEDURES

6.1. Study Measurements and Assessments

6.1.1. Assessment of Primary Endpoint

The difference in the overall and heart failure related healthcare costs between subjects treated with the Furoscix Infusor through 30 days post discharge from the emergency department compared to propensity score matched controls treated in the hospital for \leq 72 hours through 30 days post discharge. Overall and heart failure related healthcare costs comprised of all direct medical costs attributable to healthcare resource utilization incurred overall and for treatment of HF.

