6.2.7. Unscheduled Telephone Calls and Clinic Visits

There are two forms of unscheduled follow-ups specified in this protocol: telephone call and clinic visit. These may be assigned at any time at the discretion of the investigator and may arise from a request by the subject or caregiver, a request by the HF nurse, or designee, conducting telephone follow-ups, or by the judgement of the investigator. Note that the investigator can pre-specify at any time the number and timing of unscheduled follow-up visits.

If subjects experience worsening signs and symptoms they can be seen in the clinic as an unscheduled visit. For subjects presenting for an unscheduled visit the following assessments will be performed:

- Cardiopulmonary Exam including NYHA Classification
- Vital Signs
- Weight
- Labs drawn at the discretion of the investigator (including BNP or NT-proBNP)
- Assess for adverse events

All subjects will have the option to receive unscheduled phone call by an HF nurse, or designee, at any time following the initial discharge from the emergency department. The primary purpose is to respond to issues affecting proper use and administration of the Furoscix Infusor. While these calls will follow according to the aforementioned script, the HF nurse, or designee, will address - per his or her best professional judgement - specific issues reported by the patient or caregiver.

Additionally, the HF nurse, or designee, will ask (and document the responses) whether the subject has since the previous follow-up:

- Been admitted to the hospital
- Been admitted to the hospital for HF-related issues
- Been seen at the emergency department for HF-related issues
- Been seen in an outpatient clinic (including immediate care clinic) for HF-related issues
- Sought any additional or new medical treatment for HF-related issues

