3.5. Effectiveness Objective

3.5.1. Endpoints

The primary endpoint is as follows:

1. Overall and heart failure related healthcare costs of care between subjects treated with the Furoscix Infusor 30 days post discharge from the emergency department compared to propensity score versus matched controls treated in the hospital for \leq 72 hours through 30 days post discharge

The primary analysis is to compare the Furoscix Infusor (prospective arm) versus treatment as usual (historical control arm) with respect to overall cost of care and total HF-related costs. Comparison of these data between the matched (paired) cohorts will be conducted via a t-test or a Wilcoxon signed-rank test depending on the distribution of the data.

Secondary endpoints are as follows:

1. Number of hospital admissions and duration with-in 30 days post discharge from the emergency department
2. Number of HF-related hospital admissions and duration with-in 30 days post discharge from the emergency department
3. Number of HF-related emergency department visits with-in 30 days post discharge from the emergency department
4. Number of HF-related clinic visits with-in 30 days post discharge from the emergency department
5. Description of health-related quality of life using the twelve-item Kansas City Cardiomyopathy Questionnaire (KCCQ-12, for Furoscix Infusor cohort only), administered on Day 0 and Day 30.
6. Change in NT-proBNP (for Furoscix Infusor cohort only)
7. Subject and/or caregiver satisfaction with Furoscix Infusor (for Furoscix Infusor cohort only)

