3.5.3.1. Healthcare Resource Utilization (HCRU) and Costs

For each patient in the historical control and prospective arm, 30-day follow-up HF-related and all-cause healthcare resource utilization (HCRU) will be estimated and reported.

For cost inputs, events that are major contributors of the costs will be included in the analysis, including any visits and hospitalizations that are either HF-related or all-cause. Using the dataset created for matching, cost benchmarks for each event (HF-related and all-cause) i.e. mean and standard deviation will be derived. For each patient in the historical and prospective cohorts, 30-day HF-related and overall costs will be estimated by summation of applied cost benchmarks to each resource utilization event observed during the 30-day period starting from the beginning of HF-worsening episode.

Overall cost of care will include cost attribute to all-cause HCRU. Total HF-related medical costs will be comprised of the hospitalization costs and outpatient visits costs attributable to HF-related HCRU (defined by claims with a primary diagnosis of HF). All costs will be inflated to \$2019 using Medical Care Consumer Price Index (CPI). All costs included will be gross costs including payer and patient costs.

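### Overall cost needs all-cause visits in both arms, but the Furoscix-arm questions and record check itemise only HF-related ED and clinic visits

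*Protocol*

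**What the plan says.** **Endpoint.** Protocol 6.1.1 defines the cost endpoint as "all direct medical costs attributable to healthcare resource utilization incurred overall and for treatment of HF". SAP 3.5.1 compares the arms "with respect to overall cost of care and total HF-related costs".

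**How cost is built.** SAP 3.5.3.1 says that, for patients in both arms, "30-day follow-up HF-related and all-cause healthcare resource utilization (HCRU) will be estimated and reported". The events costed are the major cost contributors, "including any visits and hospitalizations that are either HF-related or all-cause". Each observed event receives a benchmark cost, and the costs are summed.

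**What Furoscix subjects are asked.** Protocol 6.2.3 to 6.2.6 each carry a heading line on interval hospitalizations, ED visits and unscheduled clinic visits, with no HF limit. The items beneath ask about any admission, but for ED visits the item is "Been seen at the emergency department for HF-related issues" and the clinic item carries the same limit. Protocol 6.2.7 (unscheduled calls) has the same items without the heading line, for example "Been seen in an outpatient clinic (including immediate care clinic) for HF-related issues".

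**What is verified.** Protocol 6.2.6: "Information regarding HF-related healthcare utilization collected before and at the 30-day in-clinic visit will be verified by the investigator" (the source is subjects' medical records).

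**Time window.** The Protocol (Synopsis, Study Assessments and Procedures; Section 2) counts 30 days from ED discharge. SAP 3.5.3.1 counts events "observed during the 30-day period starting from the beginning of HF-worsening episode".

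**The concern.** Cost is a sum over observed events, so a visit that nobody asks about adds $0. It does not appear as a missing value either, so the missing-data rule in SAP 3.3.2 would not flag it. Controls must have 3 months of continuous enrolment after index (SAP 3.5.3), and their visits are read from claims whatever the cause. If non-HF visits are captured for controls and partly missed for Furoscix subjects, overall cost differs between arms for a reason unrelated to treatment. Propensity matching on baseline variables does not correct unequal capture of the outcome.

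The itemised questions line up with secondary endpoints 1 to 4 (all admissions, HF admissions, HF ED visits, HF clinic visits). They serve those endpoints but do not fully serve the all-cause half of the primary analysis.

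**Working it through.** **1. Requirement set against capture, by event type**

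| Event within 30 days | Needed for overall cost (SAP 3.5.3.1) | Heading line (Protocol 6.2.3 to 6.2.6) | Itemised question (6.2.3 to 6.2.7) | Record check (6.2.6) |
|---|---|---|---|---|
| HF admission | yes | yes | yes | yes |
| Non-HF admission | yes | yes | yes (any admission) | not named |
| HF ED visit | yes | yes | yes | yes |
| Non-HF ED visit | yes | yes | no | not named |
| HF clinic visit | yes | unscheduled only | yes | yes |
| Non-HF clinic visit, unscheduled | yes | yes | no | not named |
| Non-HF clinic visit, routine | yes | no | no | not named |

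The gap is in three rows: non-HF ED visits and both kinds of non-HF clinic visit. Only routine non-HF clinic visits are outside every line of the contact lists.

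**2. The plan's own figure.** Inputs (Protocol 8.1, SAP 3.5.4): means $8,600 and $6,500, SD $3,045, 80% power; two-sided 5% is from SAP 3.3.3. Difference = 8,600 - 6,500 = $2,100. Per group, n = 2 × [3,045 × (1.960 + 0.842) / 2,100]² = 33.0, which rounds up to 34. A two-sample t-test gives 33.99, also 34. The stated 34 per group reproduces. The $2,100 is a hospital-cost difference and serves below only as a yardstick.

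**3. Scale, on assumed inputs.** The documents give no non-HF visit rate and no visit cost. Under-count per subject = missed visits × cost per visit. Assuming 0.1 to 0.5 missed visits at $200 to $2,000 each:
- low: 0.1 × 200 = $20, and 20 / 2,100 = about 1%
- high: 0.5 × 2,000 = $1,000, and 1,000 / 2,100 = about 48%

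The width of this range reflects the assumptions, not evidence.

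**4. What a bias of given size would do.** Assume no true difference in overall cost, SD $3,045, a fixed-sample normal approximation and 1:1 allocation, ignoring pairing and sequential boundaries. SE = 3,045 × √(2/n), which is $738 at n = 34 and $497 at n = 75. The rejection rate of a two-sided 5% test becomes:

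| Assumed bias | Share of $2,100 | 34 per group | 75 per group |
|---|---|---|---|
| $210 | 10% | 5.9% | 7.1% |
| $420 | 20% | 8.8% | 13.5% |
| $600 | 29% | 12.8% | 22.6% |

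A fixed bias matters more as the sample grows.

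**5. Window.** Protocol Section 2 and the Synopsis start at ED discharge; SAP 3.5.3.1 starts earlier, at the onset of the episode. SAP 3.5.1 itself words the endpoint from ED discharge, so the conflict is also internal to the SAP. The choice decides whether the index ED visit lies inside the costed period.

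**The case against.** The strongest reply is that the heading lines, including the one at Day 30, already require ED and unscheduled clinic visits to be assessed without an HF limit. On that reading the items beneath are examples. This largely stands. A reader might infer that the Protocol nowhere provides for collecting non-HF visits through Day 30, and the heading lines do not support that. What remains is that non-HF ED and clinic visits are not itemised, routine non-HF clinic visits are outside the word unscheduled, Protocol 6.2.7 has no heading line, and verification of non-HF use is not named.

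Other replies stand in part:
- The eCRF (SAP Appendix B) and telephone script determine actual capture, and neither is shown. SAP 3.5.3 expects all-cause ED and clinic counts for the 6 months before enrolment, which suggests such fields were contemplated, but it concerns baseline.
- The treatment-day diary item (Protocol 6.2.2) has no HF limit but covers treatment days only. Adverse events are assessed at every contact, but they record events rather than visits.
- SAP 3.5.3.1 confines costing to major contributors. Admissions, plausibly the largest item, are asked about for any cause. The same sentence still includes any visits.

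A reader might also infer that the net error must favour Furoscix. That is not established. The SAP does not say whether the two planned Furoscix clinic visits are costed. If they are, at c dollars each, they add 2c and offset an under-count u when c = u/2 (for an assumed u of $250, c = $125).

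Nor does a visit on Day 27 show a general loss of 3 days: it is one edge of a ±3-day window, and a visit on Days 30 to 33 leaves no gap.

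**Conclusion.** The point holds in limited form and should be addressed; confidence is medium. As written, the plan requires all-cause ED and clinic visits in both arms for overall cost, but in the Furoscix arm it neither itemises nor verifies the non-HF ones. Under-counting in that arm alone is a risk, not a certainty, and taken alone it would lower Furoscix overall cost. Its size cannot be derived from the documents. The $20 to $1,000 range rests wholly on assumed visit rates and costs, and the true figure may be zero if the eCRF asks more.

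It would be tempting to conclude that the main hypothesis test is compromised. The documents do not support this: the SAP null hypothesis (3.3.5, 3.5.4) concerns HF-related cost, which this scope gap leaves alone. The gap bears on the overall-cost half of the primary analysis.

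The conflict over when the 30 days start is a separate, definite contradiction, and it bears on both cost measures.

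**What to change.** 1. At every scheduled contact and unscheduled call, ask about all ED visits and all clinic visits, routine ones included, with an HF/non-HF flag.
2. Extend the existing Day 30 record check to all-cause utilization through a completed Day 30, including for subjects whose last visit falls before Day 30.
3. If the eCRF already captures these visits, say so in the SAP and align the Protocol lists.
4. If they cannot be recovered for subjects already enrolled, limit overall cost to event types captured alike in both arms.
5. State in SAP 3.5.3.1 whether protocol-scheduled clinic visits are costed.
6. Separately, choose one start for the 30-day window, use it in the Protocol and throughout the SAP, and apply it to both arms.

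The cost is wording changes to the script, visit lists, CRF and SAP, plus some extra record review at sites, which may extend to outside providers' records.

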6.2.7. Unscheduled Telephone Calls and Clinic Visits

There are two forms of unscheduled follow-ups specified in this protocol: telephone call and clinic visit. These may be assigned at any time at the discretion of the investigator and may arise from a request by the subject or caregiver, a request by the HF nurse, or designee, conducting telephone follow-ups, or by the judgement of the investigator. Note that the investigator can pre-specify at any time the number and timing of unscheduled follow-up visits.

If subjects experience worsening signs and symptoms they can be seen in the clinic as an unscheduled visit. For subjects presenting for an unscheduled visit the following assessments will be performed:

- Cardiopulmonary Exam including NYHA Classification
- Vital Signs
- Weight
- Labs drawn at the discretion of the investigator (including BNP or NT-proBNP)
- Assess for adverse events

All subjects will have the option to receive unscheduled phone call by an HF nurse, or designee, at any time following the initial discharge from the emergency department. The primary purpose is to respond to issues affecting proper use and administration of the Furoscix Infusor. While these calls will follow according to the aforementioned script, the HF nurse, or designee, will address - per his or her best professional judgement - specific issues reported by the patient or caregiver.

Additionally, the HF nurse, or designee, will ask (and document the responses) whether the subject has since the previous follow-up:

- Been admitted to the hospital
- Been admitted to the hospital for HF-related issues
- Been seen at the emergency department for HF-related issues
- Been seen in an outpatient clinic (including immediate care clinic) for HF-related issues
- Sought any additional or new medical treatment for HF-related issues

6.2.8. Cardiopulmonary Examinations

A cardiopulmonary examination will be performed consisting of assessments of the following: jugular venous distension, lungs/chest, heart, abdomen and edema.

6.2.9. BNP or NT-proBNP Assessments

BNP or NT-proBNP will be tested at all clinic visits (scheduled and unscheduled), sent to a local laboratory, and values recorded in the CRF.

6.2.10. Clinical Laboratory Tests

All routine samples will be analyzed by a local licensed clinical laboratory. The clinical laboratory tests are as follows:

- Blood clinical chemistry: Creatinine, blood urea nitrogen (BUN), sodium, potassium, chloride, bicarbonate, magnesium
- Hematology: (CBC): Red blood cell count (RBC), Total white blood cell count (WBC), Differential WBC (neutrophils, lymphocytes, monocytes, eosinophils, basophils), Hemoglobin, Hematocrit (Hct), and Platelet count
- Urine Pregnancy test: beta hCG test

The investigator is responsible for determining if out-of-range laboratory values are clinically significant or not. All clinically significant values will be followed until stabilization, resolution or loss to follow up or until no further improvement is expected.

6.2.11. Heart Failure Symptom Scoring

NYHA Functional classes will be used in this study.

Class I	- Patients have cardiac disease but without the resulting limitations of physical activity. Ordinary physical activity does not cause undue fatigue, palpitation, dyspnea or anginal pain.
Class II	- Patients have cardiac disease resulting in slight limitation of physical activity. They are comfortable at rest. Ordinary physical activity results in fatigue, palpitation, dyspnea or anginal pain.
Class III	- Patients have cardiac disease resulting in marked limitation of physical activity. They are comfortable at rest. Less than ordinary physical activity causes fatigue, palpitation, dyspnea or anginal pain.
Class IV	- Patients have cardiac disease resulting in inability to carry on any physical activity without discomfort. Symptoms of cardiac insufficiency or of the anginal syndrome may be present even at rest. If any physical activity is undertaken, discomfort is increased.

6.2.12. Vital Signs

Vital signs will include respiratory rate (respirations per minute), blood pressure (mmHg) and heart rate (beats per minute). Blood pressure and heart rate will be obtained after the Subject has been resting in sitting position for 5 minutes.

Weight and height will be collected for BMI. Height collected Day 0 only.

6.2.13. Kansas City Cardiomyopathy Questionnaire – Short Form (KCCQ-12)

The KCCQ-12 consists of 12 items pertaining to the impact of HF on quality of life. This self-administered instrument quantifies physical function, symptoms, social function, self-efficacy and knowledge, and quality of life.

6.2.14. Comfort of Wear Questionnaire

Subjects will complete a comfort of wear questionnaire at the clinic visit. The questionnaire includes questions regarding the comfort of the device while performing activities as well as subject/caregiver satisfaction with the device/study product.

6.2.15. Study Product Training

Study staff will be trained on the use of the study product, subject/caregiver considerations, and methods for training subjects and/or their caregivers who are enrolled into the study. The study staff and enrolled subjects will be trained using the Furoscix Infusor IFU and a demonstration device. The trainer will have the subject/caregivers perform the steps following the IFU. Using the demo device, subjects and their caregivers will demonstrate their ability to properly prepare and place the device prior to leaving the ED. Additionally, subjects and caregivers will receive upon discharge the IFU and subject specific instructions and will have planned and on-demand phone calls with an HF nurse, or designee, to discuss any issues.

